Appendix B Responsibilities of the Principal Investigator

1. To appropriately conduct the clinical study in compliance with this study protocol and the “Ethical Guidelines for Medical and Health Research Involving Human Subjects” and with the highest respect for human rights, safety, and welfare of study subjects.
2. To prepare a list of any other investigators and/or study collaborators when certain important study-related activities are divided by investigators and/or study collaborators, and submit the list to the sponsor as required.
3. To prepare the informed consent form and information sheet and revise it as necessary.
4. To check the contents of the study contract.
5. To provide sufficient information on the protocol, drug and duties of each personnel to investigators and study collaborators, and give guidance and supervision.
6. To select study subjects who satisfy the inclusion criteria, give explanation using written information, and obtain consent in writing.
7. To be responsible for all medical judgments related to the clinical study.
8. Corresponding to request from the chief executive of the study site, to report the latest progress status at least once a year to the chief executive of the study site.
9. To confirm and comprehend the most update status regarding the COI of the investigators participating in the clinical study according to the procedure at an affiliated study site.
10. To ensure, together with the chief executive of the study site, that sufficient medical care is provided to study subjects for all study-related clinically problematic adverse events throughout the period of subjects’ study participation and thereafter.
11. When a study subject is treated at another medical institution or department, to inform the acting physician at the medical institution or department in writing of the study subject’s study participation and study completion/discontinuation after obtaining the study subject’s consent, and prepare a record.
12. When emergency reporting of serious adverse events, etc., is required, to immediately report it in writing to the chief executive of the study site and the sponsor.
13. To prepare correct and complete CRFs, and submit them to the sponsor with an electronic signature.
14. To verify any entries on the CRFs prepared by the investigator or transcribed by the study collaborator from source data, electronically sign and submit them to the sponsor.
15. To discuss a revision of the protocol, etc., when proposed by the sponsor.
16. To report the study completion in writing to the chief executive of the study site.

10.2	Handling of Dropouts or Missing Data	13
10.3	Criteria for Interim Analysis and Early Discontinuation	13
10.4	Multicenter Studies	13
10.5	Multiple Comparisons/Multiplicity	13
10.6	Subgroup Analysis	13
11	REVISION HISTORY	15
	Appendix 1 Details of Analysis Variables	17

1 DEFINITIONS of TERMS

- Summary Statistics: Number of subjects, mean, standard deviation, maximum values, minimum values, and quartiles.
- Treatment Group: Treated with Omega-3 FAE, Not treated with Omega-3 FAE

2 TIME WINDOW

For each assessment, observation and evaluation item, evaluable data is selected according to the following table. When there are multiple data exist within a time window, the one with the closest date to the reference date is adopted, and if the differences from the reference date are the same for multiple data, the later one is adopted.

< Vital Sign, Laboratory Tests, Lipoprotein Fraction >

Time Point	Reference Date	Time Allowance
		Number of Study Days
Week 0	-1	-15~-1
Week 4	28	14~41
Week 8	56	42~70

*Treated with Omega-3 FAE: The day before study drug administration is indicated as “Day -1” and “Day 1” for the administration day.

Not Treated with Omega-3 FAE: The day of visit at Week 0 is indicated as “Day -1” and “Day 1” for the next day after the visit.

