9.3.4 Completion (Visit 4) or discontinuation

Visit 4 is the last visit, and the principal investigator or the investigator shall perform the following tests, observations, and evaluations for each study subject. If the study drug administration is discontinued, study subjects should, to the extent possible, undergo tests within 3 days from the last dose taken.

Items to be checked: Food and drink consumption before visit

- Confirm that alcohol was not consumed from 9:00 pm 2 days before the visit and food was not consumed from 9:00 pm the day before the visit
 - Confirm that excessive eating/drinking and extreme change in dietary content were not made on the day before the visit.
-
- Physical examination
 - Vital signs
 - Concomitant drugs
 - Laboratory tests
 - Treatment compliance
 - Evaluation of adverse events

At completion of the clinical study, the status of all study subjects administered the study drug shall be recorded on the CRF.

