Appendix A Schedule for Study Procedures

Visit timing	Week	Screening period	Treatment period			Discontinuation ^(e)
	Day	-4	0	4	8	
Window (day)		-29 to -1	-15 to -1	14 to 41	42 to 70	Within 3 days after the last dose
Visit No.		1	2	3	4	
Informed consent		X				
Inclusion/exclusion criteria		X				
Demographic data, medical history, previous treatment drug(s)		X				
Physical examination		X	X	X	X	X
Height		X				
Body weight		X				
BMI		X				
Vital signs		X	X	X	X	X
Concomitant drugs ^(a)		X	X	X	X	X
Concurrent disease		X	X			
Laboratory tests						
Hematology/ Serum chemistry		X ^(c)	X	X	X	X
Specific lipoprotein fraction assay ^(b)		X ^(c)	X	X	X	X
Lipoprotein assay ^(b)		X ^(c)	X	X	X	X
Mean particle diameter of LDL/HDL ^(b)		X ^(c)	X	X	X	X
Fatty acid fraction in total lipids		X ^(c)	X	X	X	X
Others		X ^(c)	X	X	X	X
Study drug prescription			X	X		
Treatment compliance				X	X	X
Food and drink consumption before the visit			X	X	X	X
Evaluation of adverse events			←X→	←X→	←X	←X

(a) All concomitant drugs will be recorded.

(b) By HPLC

(c) To be performed before the Visit 2 tests

(d) Medication will be started the day after the completion of all the tests of Week 0. The start date of medication will be referred to as Day 1.

(e) To be performed to the extent possible

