8.2 Vital Signs and Laboratory Test

8.2.1 Vital Signs

Analysis Set: Safety Analysis Set

Analysis Variables: Sitting blood pressure (Systolic, Diastolic), Sitting Pulse (bpm)

Time Point: Week 0, Week 4, Week 8

Analysis Methods: For the above analysis items, the following analysis will be performed

- (1) Summary statistics for observed value will be calculated by Time point.

Line plot of individual data will also be provided.

- (2) The same analyses described in (1) will be performed on change (Week4 /8 –Week 0) from baseline.

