8.2.2 Laboratory Test

Analysis Set: Safety Analysis Set

Analysis Variables: Hematology (Platelets)

Serum Chemistry(Total Cholesterol, TG, HDL-C, non-HDL ,
LDH, AST, ALT, ALP, γ -GTP, CK(CPK))

Category Classification: Classification by reference value

[Lower, Normal, High]

Time Point: Week 0, Week 4, Week 8

Analysis Methods: For the above analysis items, the following analysis will be performed

- (1) Summary statistics for observed value will be calculated by time point.

Line plot of individual data will also be provided.

- (2) The same analyses described in (1) will be performed on change (Week4 /8 –Week 0) from baseline.

- (3) Shift table will be reported by time point with classification above.

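### The SAP visit-window rule leaves some discontinuation samples and some first abnormal values out of the laboratory and vital-sign summaries, and no last-value or worst-value row picks them up

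*SAP*

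**What the plan says.** SAP section 2 sets one selection rule under the label "Vital Sign, Laboratory Tests, Lipoprotein Fraction". The post-baseline windows are Week 4 (Days 14-41, reference Day 28) and Week 8 (Days 42-70, reference Day 56). No window covers Days 1-13. Within a window: "When there are multiple data exist within a time window, the one with the closest date to the reference date is adopted". Ties go to the later value.

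The safety tables use that grid. SAP 8.2.1 gives "Time Point: Week 0, Week 4, Week 8" for vital signs. SAP 8.2.2 uses the same three time points for laboratory tests and adds: "Shift table will be reported by time point with classification above". Neither section has a discontinuation, last-on-treatment, worst-value or unscheduled row. SAP 10.2 rules out imputation.

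The protocol collects safety samples off that grid. Section 9.3.4 says: "If the study drug administration is discontinued, study subjects should, to the extent possible, undergo tests within 3 days from the last dose taken". Appendix A has a separate discontinuation column, timed "Within 3 days after the last dose", in which vital signs, hematology and serum chemistry are marked. Retests are not scheduled, but Protocol 10.1.2 foresees them.

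**The concern.** Picking the value nearest a target date suits an efficacy endpoint that has to be placed at Week 4 or Week 8. For safety data it can discard values that were collected precisely because something had happened. There are three ways this occurs:

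- A subject stops on Day 9 and is tested on Day 12. The sample is in no window, so the subject has no post-baseline value in SAP 8.2.1 or 8.2.2.
- A subject has Visit 3 on Day 28, stops on Day 36 and is tested on Day 38. Day 28 is 0 days from the reference and Day 38 is 10 days away, so the Day 38 sample is dropped.
- A subject has an abnormal value on Day 24 and a normal retest on Day 30. The distances are 4 and 2 days, so the retest is tabulated.

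The by-visit summaries and the reference-range shift table could then miss changes that the study measured. At the planned 25 subjects per arm, one missed shift is 1/25 = 4 percentage points of that arm.

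**Working it through.** The plan states no figure for this, so there is nothing to reproduce. I applied the SAP 2 rule day by day.

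**Inputs.** From SAP 2: windows 14-41 and 42-70, reference Days 28 and 56, nearest date wins, later value on a tie. From Protocol 9.3.4 and Appendix A: a discontinuation sample within 3 days of the last dose, on whatever day that falls. From Protocol 13.3: 25 evaluable subjects per group. Assumed, because the documents do not give it: 5% to 20% of subjects discontinue.

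**1. Discontinuation samples on Days 1-55.** Let V be the Visit 3 day.

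- Days 1-13: always excluded, 13 days.
- Days 14-41 after a Visit 3 value: the later sample is excluded if it is further from Day 28 than V is. For V from 15 to 28, the mirror day 56 - V ties and is kept, so Days 57 - V to 41 are excluded, which is V - 15 days (none for V = 14). For V above 28, every later day is further away, so 41 - V days are excluded.
- Days 14-41 with no earlier Visit 3 value: kept as Week 4.
- Days 42-55: kept as Week 8.

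| Visit 3 day | Excluded after Visit 3 | Total excluded | Share of 55 days |
|---|---|---|---|
| 14 or 41 | 0 | 13 + 0 = 13 | 24% |
| 21 or 35 | 6 | 13 + 6 = 19 | 35% |
| 24 or 32 | 9 | 13 + 9 = 22 | 40% |
| 28 | 13 | 13 + 13 = 26 | 47% |

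The largest loss occurs when Visit 3 is exactly on its target day.

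**2. From days to subjects.** Assume every discontinued subject has a sample and that it is equally likely on any of Days 1-55.

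- Low: 50 x 0.05 x 13/55 = 0.6 subjects.
- High: 50 x 0.20 x 26/55 = 4.7 subjects.

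Counting Day 56 as a possible day as well gives 0.6 and 4.6.

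**3. Retests.** Let the first value be on day d and the retest k days later in the same window, with reference day R. If d is on or after R, the retest is always further away, so the first value is kept. If d is before R, the first value is replaced when d + k - R is at most R - d, that is, when d is at most R - k/2.

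| Retest after | Week 4: first value replaced if on | Week 8: first value replaced if on | Visits within 7 days of R |
|---|---|---|---|
| 3 days | Days 14-26 (13 of 28) | Days 42-54 (13 of 29) | 6 of 15 |
| 7 days | Days 14-24 (11 of 28) | Days 42-52 (11 of 29) | 4 of 15 |
| 14 days | Days 14-21 (8 of 28) | Days 42-49 (8 of 29) | 1 of 15 |

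Across whole windows this is 28% (8/29) to 46% (13/28) of days. For visits close to target it is much less.

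**The case against.** A reader might infer that these abnormal values never reach any safety table, and that the SAP 8.2 tables are the only summary of laboratory safety. The documents do not support either. Protocol 10.1.2 makes an abnormal laboratory value an adverse event when the investigator judges it clinically problematic, and the SAP 8.1 tables of treatment-emergent events do not use the windows. A subject who stops for a raised ALT judged clinically problematic would be counted there, including under events leading to discontinuation. Adverse events are also the protocol's only safety endpoint (5.2.3). SAP 8.2.1 and 8.2.2 plan individual line plots, and SAP 9 plans listings.

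A second tempting inference is that the rule systematically hides abnormal findings in favour of omega-3. It selects on date, not on value. A first abnormal value on or after the reference day is kept and its retest is dropped, and retests can occur in both arms. Without a dropout rate, the size of any bias cannot be established.

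These points narrow the issue but do not remove it. The adverse event route depends on investigator judgement in an open-label trial, and Protocol 10.1.2 says that a retest or continued monitoring does not count as medical practice, so a value that led only to a retest need not become an event. The shift table is the summary that does not depend on that judgement. The SAP does not say whether plots and listings include out-of-window values. The SAP windows do match the visit windows in Appendix A, so this is not a contradiction; the SAP simply has no place for samples that the protocol asks for.

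The objection that a worst-value summary can itself be unbalanced also stands, and the fix has to allow for it.

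**Conclusion.** The point holds in limited form. As written, SAP 2 with SAP 8.2.1 and 8.2.2 excludes some discontinuation samples from the by-visit laboratory and vital-sign summaries and from the laboratory shift table, on 24% to 47% of the possible days before Day 56. It also replaces some first abnormal values by a retest that is as near or nearer to the reference day. The day counts follow exactly from the rule. The subject count does not: it rests on an assumed 5% to 20% discontinuation, sampling in every such subject, and an even spread of sampling days, and it may well be small at this sample size. Discontinuation samples on Days 42-70, and those on Days 14-41 with no earlier Visit 3 value, do enter the tables. This is worth correcting because a stated rule sets aside safety data already collected and the correction is cheap. It does not show that the trial's safety reporting as a whole is biased.

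**What to change.** Keep the SAP 2 windows for efficacy and for the by-visit safety rows. In SAP 8.2.1 and 8.2.2 add, by treatment group:

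1. A discontinuation/last post-baseline value row, with summary statistics and change from Week 0.
2. For laboratory tests, a worst-post-baseline shift table using all recorded values from Day 1 to the last study or discontinuation visit, scheduled or not, without window selection.

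State the direction of worst for each parameter, with separate lowest and highest shifts where both directions matter. State in SAP 8.2 and SAP 9 that line plots and listings include out-of-window values.

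The cost is SAP wording and a few extra table rows; no visits, samples or subjects are added. Unscheduled retests can be used only if they are in the study database, which the documents do not settle. The downside is that a worst-value summary picks extremes and may draw on more samples in the omega-3 arm, because discontinuation sampling is tied to the last dose. Report the number of post-baseline samples per arm beside it, and read it with the by-visit rows.

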3 ANALYSIS SET

- Full Analysis Set
The subjects who were randomized and given at least one dose of the study drug.
- Safety Analysis Set
The subjects who are given at least one dose of the study drug.

4 CONSIDERATIONS for ANALYSIS

- Significance level, Confidence coefficient
Significance level of 5%(2-sided) will be used for analysis.
Confidence coefficient of 95% (2-sided) will be used for all confidence intervals.
- Display digit
[Mean, Confidence coefficient, Quartiles]
Round to the one digits lower than significant digits of the data.

[Standard Deviation]

Round to the 2 digits lower than significant digits of the data.

[Minimum and Maximum Values]

Display the data at the significant digits.

[Proportion, Percentage]

Round to the one decimal place.

[P-value]

Round down to four decimal places. If p-value is less than 0.0001, display “p<0.0001”

5 OTHER DATA HANDLING

[Data Handling for Study Drug]

- Duration of Treatment(Treated with Omega-3 FAE)

Duration of Treatment = Date of the Last Dose – Date of the First Dose + 1

[Data Handling for Duration of Hyperlipidemia]

- Duration of hyperlipidemia (year)

Duration of hyperlipidemia (year) = (Date of first dose (year/month) – Onset/Diagnosis

Date of hyperlipidemia (year/month)) / 12 (rounded off to two decimal places)

If only the month of the onset of hyperlipidemia is unknown, the month of the onset of hyperlipidemia is regarded as “January”.

[Data Handling for Below (or Above) the limit of Quantification]

- Efficacy Data

(Laboratory Test (except Total Cholesterol, TG, HDL-C) and Lipoprotein Fraction)

Below (or equal to) the limit of Quantification: Lower Limit of Quantification to be replaced.

Above (or equal to) the limit of Quantification: Upper Limit of Quantification to be replaced.

- Safety Data

(Vital Sign and Laboratory Test (Total Cholesterol, TG, HDL-C))

Below (or equal to) the limit of Quantification: 0 to be replaced.

Above (or equal to) the limit of Quantification: Upper Limit of Quantification to be replaced.

[Data Handling for Adverse Event]

- An adverse event is defined as any untoward medical occurrence in a patient or a subject receiving a pharmaceutical product (including the study drug). It does not necessarily have an apparent causal relationship with this pharmaceutical product (including study drug). A treatment-emergent AE (TEAE) is defined as an AE which occurs after taking the first dose of trial medication.
The first dose date of “Not treated with Omega-3 FAE” is defined as the next day of the visit in Week 0.
- Time to first Onset
Time to first Onset=AE Start date - The first dose date + 1
- Related AE
AE is classified into Related/Not Related only for Treated with Omega-3 FAE group
- Non-Serious TEAEs
Non-Serious TEAE is defined as Non-Serious TEAEs of at least 5% in any treatment group by SOC and PT.

[Laboratory Test]

- (EPA+DHA)/AA Ratio
(Eicosapentaenoic Acid + Docosahexaenoic Acid)/ Arachidonic Acid
- DHA/AA Ratio
Docosahexaenoic Acid / Arachidonic Acid
- non-HDL
Total Cholesterol - HDL-C

6 SUBJECTS, DEMOGRAPHIC and OTHER BASELINE CHARACTERISTICS

6.1 Subject Disposition

6.1.1 Study Information

Analysis Set: All subjects who were obtained informed consent

Analysis Variables: The earliest date of informed consent

The latest date of the last date of administration

MedDRA Version

SAS Version

Analysis Methods: For the above analysis items, the following analysis will be performed.

- (1) Show the above items.

The latest date of the last date of administration will be presented only for treated with Omega-3 FAE.

6.1.2 Eligibility of Subjects

Analysis Set: All subjects who were obtained informed consent

Analysis Variables: Randomization into the treatment period of the study

[Yes, No (and the reason)]

Analysis Methods: For the above analysis items, the following analysis will be performed.

- (1) Summary of frequency distribution

6.1.3 Disposition of Subjects

6.1.3.1 Status at the End of Study

Analysis Set: Randomized subjects

Analysis Variables: Status at the end of study

[Complete, Incomplete (and the reason)]

Analysis Methods: For the above analysis items, the following analysis will be performed for each treatment group and all subjects in the analysis set.

- (1) Summary of frequency distribution

6.1.4 Protocol Deviations and Analysis Datasets

6.1.4.1 Protocol Deviations

Analysis Set: Randomized subjects

Analysis Variables: Protocol Deviations

[Major GCP Violations, Deviations of Protocol Entry Criteria, Deviations of Discontinuation Criteria, Deviations Related to Treatment Procedure or Dose, Deviations Concerning Excluded Medication or Therapy, Deviations to Avoid Emergency Risk, Other Deviations]

Analysis Methods: For the above analysis items, the following analysis will be performed for each treatment group and all subjects in the analysis set.

- (1) Frequency distribution

Summarize the number of subjects who have deviated from the protocol, classify the deviations into above category, and show the breakdown of deviations. Subjects applicable for multiple categories will be counted once in each category.

6.1.4.2 Datasets Analyzed

Analysis Set: Randomized subjects

Analysis Variables: Full Analysis Set [Inclusion, Exclusion]

Safety Analysis Set [Inclusion, Exclusion]

Analysis Methods: For the above analysis items, the following analysis will be performed for each treatment group and all subjects in the analysis set.

(1) Summary of frequency distribution

6.2 Demographics and Other Baseline Characteristics

6.2.1 Distribution of Demographics Items

Analysis Set; Safety Analysis Set, Full Analysis Set

Analysis Variables:

Age(Week -4)(years) [Min<= - <65, 65<=Max]

Age (Week 0) (years) [Min<= - <65, 65<=Max]

Gender [Male, Female]

Height (Week -4) (cm) [Min<= - <150, 150<= - <160,
160<= - <170, 170<= - <=Max]

Weight (Week -4) (kg)
[Min<= - <50.0, 50.0<= - <60.0,
60.0<= - <70.0, 70.0<= - <80.0,
80.0<= - <=Max]

BMI(Week -4)(kg/m²)[Min<= - <18.5, 18.5<= - <25.0
25.0<= - <=Max]

Duration of Hyperlipidemia (years) [Min<5, 5<=Max]

Frequency of Fish Intake [Almost Every Day, About Every Two Days,
About Once or Twice Per Week, Rarely]

Smoking Classification [Never Smoked, Current Smoker, Ex-Smoker]

Drink Alcohol Almost Every Day? [Yes, No]

Fasting Triglycerides(Week -4)(mg/dL)
[Min<= - <300, 300<= - <=Max]

Fasting Triglycerides (Week 0)(mg/dL)
[Min<= - <300, 300<= - <=Max]

Cholesterol Concentration in sd LDL Fraction (Week 0)

Triglycerides Concentration in sd LDL Fraction (Week 0)

Free Cholesterol Concentration in sd LDL Fraction (Week 0)

Phospholipid Concentration in sd LDL Fraction (Week 0)
Particle Size (nm) of LDL (Cholesterol Monitor) (Week 0)
Particle Size (nm) of LDL (Triglycerides Monitor) (Week 0)
Particle Size (nm) of LDL (Free Cholesterol Monitor) (Week 0)
Particle Size (nm) of LDL (Phospholipid Monitor) (Week 0)

Analysis Methods: For the above analysis items, the following analysis will be performed for each treatment group and all subjects in the analysis set.

- (1) Summary of frequency distribution for discrete variables and summary statistics for continuous variables.

6.2.2 Medical History and Concurrent Medical Conditions

Analysis Set: Safety Analysis Set

Analysis Variables: Medical history, Concurrent medical conditions

Analysis Methods: For the above analysis items, the following analysis will be performed for each treatment group. Analysis variables will be coded using the MedDRA dictionary and be summarized into SOC and PT. SOC's will be sorted in alphabetical order, then PTs will be sorted in frequency order.

- (1) Medical history: Summary of frequency distribution by SOC/PT
- (2) Concurrent medical conditions: Summary of frequency distribution by SOC/PT

The method of accounting for the frequency is as follows.

[Number of subjects with AE]

For each summary, subjects with one or more events within a level of SOC term is counted only once in that level. Similarly, subjects with one or more events within a level of PT term is counted only once in that level.

